**DR. [name]**  
**BM (University of Southampton, UK)**

**UNIVERSITI KEBANGSAAN MALAYSIA**

## **INTRODUCTION**

Regional anaesthesia is one of the mainstays of anaesthesia methods in various disciplines particularly orthopaedic surgeries. Patient communication intra-operatively is one of its main forte, not to mention reduced cost with less complications and faster patient recovery. However, the state of consciousness can potentially cause patient anxiety and non-cooperation which may interfere with surgery, therefore reduce surgeon and patient satisfaction. Sedation has an essential role in balancing the pros and cons of regional anaesthesia.

Sedation has its spectrum ranging from anxiolysis to deep sedation. Within this range, conscious sedation or monitored anaesthesia care sedation is usually provided by the anaesthetist to supplement regional anaesthesia. It aims for a comfortable and pain-free patient who is sedated but remains arousable, able to obey commands and maintain their airway independently. However, it is difficult to judge precisely the amount of sedative required for adequate patient sedation, comfort and analgesia as patients' needs differ.

Propofol remains the most attractive choice of drug for sedation due to its favourable pharmacokinetic profile, which results in fast induction, easy control of depth of sedation and rapid recovery. Apart from its rapid onset and offset, propofol has anxiolytic, amnesic and anti-emetic effects, making it the nearest to ideal agent for sedation during surgery under regional anaesthesia. Propofol can be infused by a manually controlled volumetric infusion pump, or targeted to a specific plasma or effect site concentration using target-controlled infusion (TCI) devices. Target-controlled infusion allows the anaesthetist to set the desired target plasma or effect site concentration and the TCI pump adjusts infusion rate according to the pharmacokinetic model of the drug. Target-controlled infusion improve drug titration as it better matches the drug concentration profile to the rapidly changing intra-operative drug requirement compared to manually controlled infusion.

Patient-controlled sedation (PCS) is a valid option for surgeries or procedures under regional anaesthesia. It is a well-established technique, initially adapted from post-surgery patient controlled analgesia. First reported in 1991, Rudkin et al studied PCS with propofol in patients undergoing dental extractions under local anaesthesia. Park and Watkins studied the efficacy of anaesthetist-controlled sedation (ACS) versus PCS, both using bolus delivered

midazolam and fentanyl, in patients undergoing lower extremity and lower abdominal procedures under epidural anaesthesia. In both studies, PCS resulted in significant satisfactory response from the patients. In 2000, Girdler et al reported that patients utilizing PCS with propofol reached target sedation faster, though not significant, than patients with ACS of continuous propofol infusion in surgeries under local anaesthesia. In 2008, Wahlen et al reported significantly lower plasma and effect-site propofol concentration with high degree of patient satisfaction among patients on PCS compared to ACS of continuous propofol infusion in patients undergoing total knee and hip replacements under spinal anaesthesia.

This study aims to compare the effectiveness of ACS using TCI sedation (TCIS), versus PCS in patients undergoing lower limb orthopaedic surgery under central neuraxial block (CNB). If PCS could be shown to be superior in terms of reduced propofol requirement, in addition to improved safety, sedation quality and patient satisfaction, it could be an alternative sedation option, or replace ACS as the current means of sedation in surgeries under CNB.

## **OBJECTIVES**

### **Primary objective**

To compare total propofol requirement between propofol sedation using patient-controlled sedation versus target-controlled infusion, in patients undergoing lower limb orthopaedic surgery under central neuraxial block.

### **Secondary objective**

To compare complications, sedation quality and patient satisfaction.

## **MATERIALS AND METHODS**

This prospective, randomised clinical trial will be submitted for approval from the Research Committee of the Department of Anaesthesiology & Intensive Care, Universiti Kebangsaan Malaysia Medical Centre (UKMMC) and the Medical Research & Ethics Committee, UKMMC. Once ethical approval has been obtained, the subjects will be screened by the principal investigator during the pre-operative visit. Patient inclusion and exclusion criteria include:

### **Inclusion Criteria:**

1. American Society of Anesthesiologists (ASA) I or II.
2. Aged 18-65 years.
3. Elective lower limb orthopaedic surgery under CNB anticipated to last for 1.5 to 2 hours

### **Exclusion Criteria:**

1. Body Mass Index (BMI)  $> 30\text{kg/m}^2$
2. Unable to cooperate (eg. mental disorders, language barrier)
3. Drug abuse
4. Alcoholism (chronic daily alcohol intake greater than 75 g of pure alcohol for  $\geq 2$  years, where 75g of alcohol = 5 cans of beer, 1 bottle of wine or half a pint of distilled spirit)
5. Contraindications to the study drugs
6. Pregnancy
7. Significant pulmonary or cardiovascular diseases, including Obstructive Sleep Apnoea (OSA) and Obesity Hypoventilation Syndrome (OHS)
8. Features of difficult airway

During the pre-operative visit, the patient will be briefed on the study and informed consent obtained. They will also be assessed for pre-operative anxiety by using the Amsterdam Pre-operative Anxiety and Information Scale (APAIS; Appendix 1), where only the anxiety components of the original questionnaire will be assessed. Patients will be graded on a five-point Likert scale from 1 = not at all, to 5 = extremely anxious. A patient with score  $\geq 11$  is considered anxious.

All patients will be given pre-medication of oral midazolam 3.75 or 7.5 mg accordingly. Subjects will be randomised via computer generated block randomisation into Group PCS and Group TCIS. The study will be conducted by multiple anaesthesia medical officers. In the operating theatre, standard monitoring will include electrocardiogram (ECG), non-invasive blood pressure, pulse oximetry and transthoracic impedance pneumography. Baseline readings will be recorded. Intravenous access will be established with an 18G cannula and normal saline 0.9% infused.

Central neuraxial block will be performed under aseptic technique by the anaesthesia medical officer in-charge and the L2-3 or L3-L4 intervertebral space sought with the patient sitting. The subarachnoid space will be located using a pencil 27G (B Braun, Germany) spinal needle and hyperbaric bupivacaine 0.5% plus fentanyl 15-25 µg will be administered. In the case of combined spinal-epidural anaesthesia (CSE), the epidural space will be located with a Tuohy 18G epidural needle, and the epidural catheter secured in place (Espocan®, B Braun, Germany). After establishing an adequate sensory level, surgery will be allowed to proceed, and PCS or TCIS commenced. Patients with failed subarachnoid block or sensory block inadequate for surgery will be dropped out from the study. All patients will receive oxygen supplement of 5L/min via a face mask. Heart rate (HR), blood pressure (BP), oxygen saturation (SpO2) and respiratory rate (RR) will be monitored and documented every 5 minutes. Patients will be kept warm with standard intra-operative warming devices during the surgery.

Propofol will be premixed with lignocaine where 10 mg of lignocaine will be added to every 100 mg propofol 1% to reduce the intensity of pain on injection with propofol. Patients in Group PCS will receive intravenous (IV) propofol (Lipuro® 1%, B.Braun, Germany) via a Graseby® Omnifuse patient controlled analgesia (PCA) (Smith's Medical, UK) infusion pump. The machine will be set to deliver a demand bolus dose of 0.25 mg/kg with no lockout interval or basal infusion. The patient will be instructed to press on a hand-held device as often as required to achieve their desired level of comfort or sedation. The sedation level will be assessed using the Observer's Assessment of Alertness/Sedation Scale (OAA/S; Appendix 2) every 5 minutes in the first 30 minutes, followed by every 20 minutes thereafter.

Patients in Group TCIS will receive IV propofol (Lipuro® 1%, B.Braun, Germany) via a Graseby® Omnifusion target-controlled infusion (TCI) pump (Graseby Medical, Watford,

U.K) targeting an initial effect site concentration (Cet) of 0.6 µg /ml, using the Schnider pharmacokinetic model. Upon attainment of 0.6 µg /ml Cet, the patient's sedation level will be assessed. The Cet will be increased or reduced accordingly by 0.2 µg/ml to attain an OAA/S score of 3. After equilibrium between predicted and set concentration is achieved, OAA/S score is re-assessed and adjustment of Cet is made until OAA/S score of 3 achieved. The induction time, which is the time taken to reach OAA/S of 3, will be documented in both groups. Thereafter the OAS/S will be assessed every 20 minutes.

Complications from sedation will be managed as follows:

1. Hypotension (systolic BP 20% below baseline) will be treated with administration of IV fluid and titrated bolus doses of IV ephedrine 6 mg or IV phenylephrine 100 µg as required.
2. Bradycardia (HR < 40bpm) will be treated with IV atropine 0.6mg.
3. Respiratory depression (RR < 8 breaths/min) and oxygen desaturation (SpO2 < 95%) will be managed by verbal or tactile stimuli, and titrating down Cet by 0.2 µg/ml in the TCI group, delivering 100% oxygen by applying airway maintenance manoeuvres and assisted ventilation as necessary.
4. Over-sedation (OAS/S score ≤ 2) will be managed by verbal or tactile stimuli, and titrating down Cet by 0.2 µg/ml.

The use of airway adjuncts or intubation will be considered depending on the severity of respiratory compromise. These patients will be excluded from analysis of recovery characteristics.

Sedative administration will be terminated (T0) at the completion of surgery. At the recovery area, standard monitoring will be employed. The medical officer in the recovery room will assess the OAS/S score every 5 minutes. The recovery time, which is the time taken to reach OAS/S 5 from T0 will be documented. Total propofol requirement in both groups will be calculated in mg/kg/hour.

Before discharge from the recovery room, patient satisfaction with sedation was measured using a 10-point verbal rating scale, 1 being extremely dissatisfied and 10 being extremely satisfied.

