### **Statistical tests**

Demographic data and total propofol requirement will be analysed using the student's t-test (or Mann Whitney-U test for non-parametric data). Patients' satisfaction score will be compared using the student's t-test. The satisfaction level of anxious patients in PCS group and TCIS group is compared by using the t-test. A p-value  $< 0.05$  will be considered statistically significant.

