### FLOW CHART

**DATA COLLECTION FORM**

Study ID:					Study group	 PCS  TCIS
Age:		Gender:		Race:		
Height (m):		Weight (kg):		BMI:		ASA:
Diagnosis:				Surgical procedure:		

Time surgery commenced:

Time sedation commenced:

Time to reach OASS score 3: \_\_\_\_\_ min

Time surgery ended:

Time sedation terminated (To):

Total propofol requirement: \_\_\_\_\_ mg

Time of arrival at the recovery room:

Time to reach OASS score 5: \_\_\_\_\_ min

Time discharged from recovery room:

COMPLICATIONS	YES	NO	RESCUE/REMARKS
Systolic BP < 20% baseline			
HR < 40 bpm			
RR < 8/min			
SpO 2 < 95%			
OAS/S ≤ 2			

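### Midazolam premedication is given at one of two doses, but the plan does not fix the dose before allocation, provide for recording it, or adjust the propofol comparison for it.

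*Combined protocol and SAP*

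**What the plan says.** All of this is in the combined protocol and SAP.

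- **Premedication** (Materials and Methods, text after the Exclusion Criteria): "All patients will be given pre-medication of oral midazolam 3.75 or 7.5 mg accordingly". The higher dose is twice the lower (7.5 / 3.75 = 2). The last word of the sentence is the only guidance on who gets which; weight, age and anxiety score are not named as criteria.
- **Randomisation** (the next sentence): "Subjects will be randomised via computer generated block randomisation into Group PCS and Group TCIS". No stratification factor is named. Then: "The study will be conducted by multiple anaesthesia medical officers". The readable text describes neither blinding nor allocation concealment.
- **Intrathecal drugs** (same section): "hyperbaric bupivacaine 0.5% plus fentanyl 15-25 µg will be administered". The fentanyl dose is therefore also a range.
- **Primary outcome**: "Total propofol requirement in both groups will be calculated in mg/kg/hour".
- **Analysis** (Statistical tests): "Demographic data and total propofol requirement will be analysed using the student's t-test (or Mann Whitney-U test for non-parametric data"). No covariate is listed, and no comparison of premedication between arms.
- **Data collection form**: demographics, ASA, diagnosis, procedure, times (such as "Time sedation commenced"), "Total propofol requirement" in mg, and five complications. The monitoring chart has BP, HR, SpO2, RR, OAS/S and Cet. Neither prints a field for midazolam dose, midazolam time or fentanyl dose.

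**The concern.** The primary outcome is the amount of one sedative used by patients who have all been given another. Both arms work by feedback: in TCIS the propofol target is moved until OAA/S reaches 3, and in PCS the patient presses until comfortable or sedated as desired. A sedative already on board could plausibly change how much propofol is used, as well as induction time, over-sedation and recovery time.

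The stake depends on when the dose is chosen.

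- **Before allocation.** The dose is an ordinary baseline variable. Leaving it out costs some precision and a row in the baseline table.
- **With the arm known.** The dose could follow the arm, and part of any propofol difference would then reflect premedication. With no provision to record the dose, the trial's data could neither reveal this nor correct it.

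The premedication sentence precedes the randomisation sentence, but nothing states that the events happen in that order.

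**Working it through.** **Inputs from the Sample size calculation section:** alpha 0.05, power 80%, difference 0.5 mg/kg/hour, SD 0.74, ratio 1:1, 35 per group, 78 in total after 10% drop-out.

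**Inputs assumed, because the documents give none:** half the patients on each dose; a dose effect B on propofol use of 0 / 0.2 / 0.3 / 0.5 mg/kg/hour, already contained in the SD of 0.74.

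**1. The plan's own figure.** n per group = 2 × (0.74 × (1.96 + 0.842) / 0.5)² = 34.4, rounded up to 35, which agrees with the plan. The noncentral-t calculation gives 35.4, so 36. Inflating for drop-out, 35 / 0.9 = 38.9, so 39 per group and 78 in total. These agree.

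**2. Chance imbalance in the share on the higher dose (dose set before allocation).**
- SE = sqrt(2 × 0.5 × 0.5 / 35) = 0.120, or 12 percentage points; 95% range ±1.96 × 0.120 = ±23 points.
- At 35 per arm, 20 points is a difference of 7 patients. The exact binomial probability of a difference of 7 or more is 12.0%.
- At 39 per arm the SE is 11.3 points, 20 points needs a difference of 8 patients, and the probability is 8.9%.

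These treat the two arms as independent binomial samples.

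**3. What adjustment would gain.** Share of variance explained = 0.25 × B² / 0.74². Residual SD = 0.74 × sqrt(1 − share). Power is by noncentral t at 35 per arm, ignoring the single degree of freedom spent.

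| Assumed B (mg/kg/hour) | Variance removed | Residual SD | Power |
|---|---|---|---|
| 0 | 0% | 0.74 | 80% |
| 0.2 | 2% | 0.73 | 80% |
| 0.3 | 4% | 0.72 | 81% |
| 0.5 | 11% | 0.70 | 84% |

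**4. If the dose followed the arm.** A systematic imbalance d shifts the arm difference by B × d. The SE of the arm difference is 0.74 × sqrt(2/35) = 0.177. With s = B × d / 0.177, the actual two-sided error at a nominal 5% is Φ(−1.96 + s) + Φ(−1.96 − s).

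| Assumed B | d = 20 points: shift (share of 0.5), error | d = 40 points: shift (share of 0.5), error |
|---|---|---|
| 0 | 0 (0%), 5% | 0 (0%), 5% |
| 0.2 | 0.04 (8%), 6% | 0.08 (16%), 7% |
| 0.3 | 0.06 (12%), 6% | 0.12 (24%), 10% |
| 0.5 | 0.10 (20%), 9% | 0.20 (40%), 20% |

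Nothing in the documents shows that such an imbalance would occur. The table gives only its consequence if it did.

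**The case against.** A reader might infer several stronger things that the documents do not support.

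- **That the dose is certainly not captured.** The printed form also has no field for the APAIS score or the satisfaction rating, yet the protocol collects both and the Statistical tests section relies on both. The form is therefore not a full list of what is collected. The dose might also be recoverable from hospital drug charts. The most that can be said is that no provision to record it is stated.
- **That a chance imbalance would invalidate the comparison.** It would not. If the dose precedes allocation, randomisation covers it like any other baseline factor, and the 5% error rate already allows for chance differences.
- **That arm-dependent dosing is happening, or differs between sites.** One centre is named, and the text mentions premedication before randomisation. This route is open only because the order is not stated and no concealment is described.
- **That midazolam is an established determinant of propofol need here.** The documents do not say so. If the dose is chosen by weight or anxiety, its association with a weight-normalised rate could be near zero or of either sign. That is why zero is in the range above.

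All four points stand. It is also fair to say that the gain in precision is small for most of the assumed range. None of this removes the case for fixing and recording, in a trial of sedative requirement, a sedative dose left to discretion.

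**Conclusion.** The concern holds as a gap in the plan, not as a demonstrated bias. Three things are missing: a statement that the midazolam dose is settled before the arm is known, a stated provision to record it, and an analysis that uses it.

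On the benign reading the primary test is valid and the loss is modest: power moves from about 80% to at most 84% over the assumed effects, and the trial cannot show that the arms were balanced on premedication. On the other reading, which the text leaves open, the primary comparison could be biased without trace. For a 20-point imbalance and an assumed effect of 0.5, the shift would be a fifth of the planned difference.

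Every size quoted rests on an assumed dose effect and an assumed 50:50 split. The change is worth making because it is cheap and closes the bias route by design.

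**What to change.** 1. **Materials and Methods, premedication and randomisation.** State that the midazolam dose is decided and written on the form before the allocation is opened. The clinical choice of dose stays as it is.
2. **Data collection form.** Add fields for midazolam dose and time given. Add the intrathecal fentanyl dose for description only: in the order of the text it is given after randomisation, so it should not be treated as a baseline covariate.
3. **Statistical tests.** Tabulate midazolam dose by arm. The section has no model to which a covariate could be added, so name one: a linear model (ANCOVA) of propofol mg/kg/hour on arm and midazolam dose (two levels). If the data are non-normal, use a van Elteren test stratified by midazolam dose in place of the Mann-Whitney test.

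The cost is a few form fields and one degree of freedom. No extra patients are needed and patient care does not change.

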## **STATISTICAL ANALYSIS**

### **Sample size calculation**

The  $\alpha$  value is set at 0.05 and power of study at 80%. Sample size calculation was based on mean propofol requirement for sedation in a study by Singh T *et al.* We expect a difference of 0.5 mg/kg/hour of propofol between Groups PCS and TCIS.

The sample size was calculated using the 'Power and Sample Size Calculations' program.

Sample size calculated using t- test.

Requested output: Sample size

Independent

Alpha = 0.05; power = 0.8;  $\delta = 0.5$ ;  $\sigma = 0.74$ ; M = 1

Case sample size for t-test = 35

[figure not shown]
Total sample size: 35 x 2 plus 10% drop-out rate = 78

Sample size = 39 per study group.

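### Anxiety class (APAIS 11 or more) defines a planned between-arm satisfaction test, but it is neither a randomisation stratum nor a covariate in any analysis; the cost is modest and cheap to avoid

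*Combined protocol and SAP*

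**What the plan says.** In Materials and Methods, the text after the exclusion criteria describes the pre-operative visit, where patients are briefed and consent is taken. Of the same visit it says: "They will also be assessed for pre-operative anxiety". Only the anxiety items of the APAIS are used, and a score of 11 or more classes a patient as anxious. The next paragraph covers premedication and then allocation: "Subjects will be randomised via computer generated block randomisation into Group PCS and Group TCIS". It gives no stratification factor and no block size.

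The Statistical tests section contains one subgroup comparison: "The satisfaction level of anxious patients in PCS group and TCIS group is compared by using the t-test". The other tests listed there are unadjusted two-group tests (t-test, or Mann-Whitney for non-parametric data). APAIS enters none of them as a covariate.

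The Sample size calculation rests on propofol requirement alone: "We expect a difference of 0.5 mg/kg/hour of propofol between Groups PCS and TCIS". The plan gives neither an expected number of anxious patients nor a power for the comparison among them.

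**The concern.** Unstratified blocks keep the two arms equal in size overall. They do not keep the anxious patients evenly divided. Two things follow.

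- **Within the subgroup.** An uneven split makes the planned satisfaction test less precise than the same number of anxious patients could give.
- **Across the whole trial.** The arms can differ by chance in the share of anxious patients. In the PCS arm, patients press on demand with no lockout. It is therefore plausible, though the documents do not show it, that anxiety influences propofol use, the primary endpoint, as well as satisfaction. With no adjustment planned, such an imbalance would go straight into the unadjusted comparisons.

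The trial already measures this factor, already dichotomises it and already singles it out for analysis. Using it in the design or the models needs no new assessment.

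**Working it through.** **The plan's own figure.** The inputs from the Sample size calculation are a difference of 0.5 and an SD of 0.74 mg/kg/hour, with alpha and power given as "value is set at 0.05 and power of study at 80" (per cent). Sidedness is not stated; two-sided reproduces the result.

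n per arm = 2 × (1.960 + 0.842)² × 0.74² / 0.5² = 2 × 7.85 × 0.5476 / 0.25 = 34.4, rounded up to 35. This agrees with "Case sample size for t-test = 35". With 10% drop-out, 70 / 0.9 = 77.8, rounded up to 78, or 39 per arm. The total is not in dispute. It was set for the primary endpoint and says nothing about the subgroup.

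**Assumption.** The share of anxious patients is not in the documents. I take 15%, 20%, 30% and 40% of 78, which gives m = 12, 16, 23 and 31.

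**Formulas.** With arms of 39 and no stratification, the number k of anxious patients in one arm is hypergeometric:

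P(k) = C(39, k) × C(39, m − k) / C(78, m)

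Simulated unstratified blocks of 4 and 6 gave nearly the same split probabilities.

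The variance of a difference in means is proportional to 1/k + 1/(m − k). Relative to an even split, the inflation is m² / [4k(m − k)]. For example, a 4:8 split of 12 gives 144 / (4 × 32) = 1.125. Averaging over P(k) gives the mean inflation VI, and the information lost, in patients, is m − m/VI.

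The difference between arms in anxious share is |2k − m| / 39. It reaches 10 percentage points when the counts differ by 4 or more (4/39 = 10.3%).

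| m | Chance of a 2:1 or worse split | Mean variance inflation | Patients' worth lost | Chance that shares differ by 10 points or more |
|---|---|---|---|---|
| 12 | 35% | 9% | 1.0 | 35% |
| 16 | 16% | 6% | 0.9 | 40% |
| 23 | 5% | 3% | 0.8 | 32% |
| 31 | 2% | 2% | 0.6 | 35% |

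The 35% for a 2:1 split at m = 12 counts the exact 4:8 split. The chance of anything worse than 2:1 is 11%.

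**What stratification would recover.** For each m, take the standardised difference that a two-sided t-test detects with 80% power at an even split, then average the power over P(k).

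| m | Detectable difference, even split (SD) | Average power without strata |
|---|---|---|
| 16 | 1.51 | 77.8% |
| 23 | 1.23 | 78.8% |
| 31 | 1.04 | 79.2% |

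The gain is 80 − 77.8 = 2.2 points at m = 16 and 80 − 79.2 = 0.8 points at m = 31. If only 8 patients were anxious, average power would be 74.3%, a gain of about 6 points, but the detectable difference would then be 2.38 SD.

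**The case against.** The strongest case against is that this is a preference, not a defect. The loss in the subgroup is about one patient. The most striking split probability depends on the lowest assumed prevalence and on counting a tie. The comparison rests on one sentence in the Statistical tests section: the secondary objective names patient satisfaction but not anxious patients. No passage links APAIS to propofol use or satisfaction. Two lists leave two incomplete blocks and make allocation somewhat easier to guess in a small stratum. Patients with a failed or inadequate block are dropped, so the analysed split can drift anyway. Chance imbalance can be handled by covariate adjustment without touching the randomisation.

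Most of this stands, and it sets the size of the point. The last argument supports the first half of the fix, because no such adjustment is planned.

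Three stronger readings are tempting, and the documents support none of them:

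- **A reader might infer that the subgroup test is biased.** It is not. Allocation remains random among anxious patients, so an uneven split costs precision only.
- **A reader might infer that stratifying would rescue the subgroup test.** It would not. Even a perfectly even split leaves a detectable difference above 1 SD throughout the assumed range.
- **A reader might take a small subgroup, and scoring before allocation, as documented.** Both are inferences. The plan gives no prevalence, and the timing follows only from the pre-operative visit and the order of the text.

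**Conclusion.** The point holds as an optional improvement. The plan singles out a baseline class for a between-arm test but uses it neither in the allocation nor in any model. For the subgroup, the expected cost is a mean variance inflation of about 2% to 9%, roughly one patient's worth of information, if 12 to 31 of 78 patients are anxious. For the whole trial, an imbalance of 10 or more percentage points in anxious share has a chance of about 32% to 40% over that range. How much that matters depends on how strongly APAIS predicts propofol use and satisfaction, which the documents do not say. Nothing here makes a planned comparison invalid or calls the total of 78 into question.

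**What to change.** 1. In Statistical tests, add APAIS (score or class, chosen in advance) as a covariate in the whole-trial comparisons of propofol requirement and satisfaction, for example in a linear model with arm and APAIS. This can be done even if the randomisation lists already exist, and it costs a sentence. The data collection form as reproduced shows no APAIS entry, so check that the score reaches the dataset.
2. If the lists are not yet generated, produce one block list for APAIS below 11 and one for 11 or more, with varying block sizes. State that the score is recorded before allocation. The sample size is unchanged. The cost is a second list, and slightly more predictable allocation in a small stratum if block sizes are fixed.
3. Describe the anxious-patient t-test as exploratory, since neither step gives it adequate power.

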**Monitoring chart**

Time (min)	Baseline	5	10	15	20	25	30	35	40	45	50	55	60	65	70	75	80	85	90	95	100	
BP (mmHg)																						
HR (bpm)																						
SpO2 (%)																						
RR(per min)																						
OAS/S score																						
Cet (ng/ml) *TCIS only																						

Time (min)		105	110	115	120	125	130	135	140	145	150	155	160	165	170	175	180	185	190	195	200	
BP (mmHg)																						
HR(bpm)																						
SpO2 (%)																						
RR(per min)																						
OAS/S score																						
Cet (ng/ml) *TCIS only																						

(OAS/S charting for PCS: Every 5 mins for 30 mins, thereafter every 20 mins. TCIS: Adjustent of targeted effect site concentration until OASS score 3, thereafter every 20 mins)

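### OAA/S is scored on a different timetable in each arm, so the per-case over-sedation tick (OAA/S ≤ 2) is ascertained differently in PCS and TCIS; the effect is minor and its direction is unknown

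*Combined protocol and SAP*

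**What the plan says.** **PCS.** Materials and Methods puts this arm on a fixed clock, with OAA/S scored "every 5 minutes in the first 30 minutes, followed by every 20 minutes thereafter". Dosing is by patient demand, with "no lockout interval or basal infusion".

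**TCIS.** Scoring follows the titration. When the first target is attained, the "sedation level will be assessed. The Cet will be increased or reduced accordingly by 0.2" µg/ml. Then: "After equilibrium between predicted and set concentration is achieved, OAA/S score is re-assessed". This cycle continues until OAA/S 3. No clock interval is given for it. After that, "Thereafter the OAS/S will be assessed every 20 minutes".

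The last sentence follows one about both groups, so on its own it could be misread as a common rule. The footnote to the monitoring chart removes the doubt by giving each arm its own schedule: "OAS/S charting for PCS: Every 5 mins for 30 mins, thereafter every 20 mins" for one, and for TCIS target adjustment "until OASS score 3, thereafter every 20 mins".

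**Outcome.** The secondary objective is "To compare complications, sedation quality and patient satisfaction". Over-sedation is defined as OAA/S ≤ 2 and is one of five complication items on the data collection form, each ticked yes or no for the case, with a column for rescue and remarks. The other four items rest on blood pressure, heart rate, respiratory rate and SpO2, which are documented every 5 minutes in all patients. The Statistical tests section names no test for complications.

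**The concern.** A yes/no outcome that is read off a scale at set times depends on how often, and when, the scale is read. Over-sedation is the only one of the five complication items whose reading times depend on the arm. A TCIS patient who reaches OAA/S 3 early moves to 20-minute scoring while a PCS patient is still scored every 5 minutes. A TCIS patient with a long titration and frequent checks may be scored more often than a PCS patient.

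The Introduction makes improved safety and sedation quality part of the case for PCS as an alternative to, or replacement for, anaesthetist-controlled sedation. A difference in over-sedation that came partly from the scoring timetable could be read as a difference between the techniques, and it could not be corrected after the event.

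**Working it through.** **The plan's own calculation.** The only computed figure is the sample size for propofol requirement. With δ = 0.5, σ = 0.74, two-sided α = 0.05 (sidedness assumed) and power 0.80, the normal formula 2(1.960 + 0.842)² × 0.74² / 0.5² gives 34.4, so 35 per group. Then 70 / 0.9 = 77.8, so 78. The plan's figures reproduce and do not enter this point.

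**Inputs from the documents.** The two timetables above; surgery expected to last 1.5 to 2 hours, so case length T = 90 or 120 min; 39 per group.

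**Assumptions (not in the documents).** Both clocks start with sedation. TCIS titration checks come every g = 2.5 or 5 min until OAA/S 3 at time t = 5 to 30 min. There is one episode of length d per patient, with onset uniform over the case. Only scheduled looks count.

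**Formula.** An episode is detected if a look falls within d minutes after onset. Detection = (minutes of the case lying within d before some look) / T. If looks are at least d apart and the first is at d or later, this is (number of looks × d) / T.

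**Worked cases, T = 90, equal episodes.**
- PCS looks: 5, 10, 15, 20, 25, 30, 50, 70, 90 (nine). For d = 5: 9 × 5 / 90 = 0.50.
- TCIS, t = 5, g = 5: looks at 5, 25, 45, 65, 85 (five). 5 × 5 / 90 = 0.278; ratio 1.80.
- TCIS, t = 10, g = 5: looks at 5, 10, 30, 50, 70, 90 (six). 6 × 5 / 90 = 0.333; ratio 1.50.
- TCIS, t = 30, g = 5: same looks as PCS; ratio 1.00.
- d = 2, g = 2.5, t = 30: TCIS has twelve looks to 30 min plus 50, 70, 90. 15 × 2 / 90 = 0.333, against PCS 9 × 2 / 90 = 0.20; ratio 0.60.

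**PCS:TCIS detection ratios.**

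| Episode length | Checks and time to OAA/S 3 | T = 90 | T = 120 |
|---|---|---|---|
| 5 min, both arms | g = 2.5 or 5, t = 5–20 | 1.3–1.8 | 1.1–1.7 |
| 10 min, both arms | g = 2.5 or 5, t = 5–20 | 1.2–1.3 | 1.0–1.3 |
| 20 min, both arms | g = 2.5 or 5, t = 5–20 | 1.0–1.2 | 0.9–1.05 |
| 2 min, both arms | g = 2.5, t = 5–20 | 0.8–1.5 | 0.8–1.4 |
| 2 min, both arms | g = 2.5, t = 25–30 | 0.60–0.69 | 0.62–0.71 |
| PCS 5 min, TCIS 10 min | g = 2.5 or 5, t = 5–20 | 0.9–1.0 | 0.7–0.9 |

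**Where the difference arises (d = 5).** For onset in the first 30 min, PCS detects 1.00 and TCIS 0.33 to 0.67 (t = 5–20). For onset after 30 min, detection is 0.25 in both arms at T = 90, and 0.22 against 0.22–0.28 at T = 120.

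**In patients.** Assume a true risk of 20% in both arms, 39 per arm, d = 5 and t = 10. At T = 90: 39 × 0.20 × 0.50 = 3.9 recorded in PCS and 39 × 0.20 × 0.333 = 2.6 in TCIS. At T = 120: 39 × 0.20 × 0.417 = 3.3 and 39 × 0.20 × 0.292 = 2.3. At these rates Fisher's exact test at 0.05 would reject in about 2.5% and 1.5% of trials.

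**The case against.** The timetables differ on purpose. TCIS scoring is the feedback step of a titration to OAA/S 3; PCS has no such target and needs a clock. The chart footnote repeats both schedules, so the protocol does not contradict itself. That stands, but it explains why TCIS has extra checks, not why outcome recording lacks a common timetable.

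The model rests on inputs the documents do not give. The complications form is not tied to scheduled scores, and over-sedation is to be managed when it occurs, so unscheduled observations may be ticked, which would shrink the gap. TCIS checks follow target changes; if risk clusters there, uniform onset understates TCIS detection. Whether a later target reduction brings a further equilibrium check is not stated, and the model assumes none. All of this stands, and it is why no single ratio should be quoted.

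Two stronger readings are tempting, and neither is supported:
- A reader might infer that PCS will usually record more over-sedation. That needs equal risk, equal episode length, scheduled looks only and a fairly short titration, none of which the documents establish. Demand boluses and a held target may well produce episodes of different length, and the ratio reverses under some inputs even with equal episodes.
- A reader might take the first-30-minute contrast (1.00 against 0.33–0.67) as the size of the problem. The plan has no separate early count; those events only feed one whole-case tick.

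Finally, no test is named for complications and the likely harm is small. That stands, and sets the severity.

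**Conclusion.** The point holds as a minor one. Followed as written, the plan gives arm-dependent ascertainment of over-sedation within a between-arm secondary objective, and nothing in it reconciles the schedules. The equal-episode ratio of about 0.6 to 1.8 marks out what the assumptions allow; it does not estimate the bias, and its direction cannot be settled from the documents. The consequence is a possibly distorted description of one of five complication items, not a material risk of a false positive test. The other four items are recorded every 5 minutes in both arms, and neither the sample size nor the measurement of propofol requirement is touched.

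**What to change.** For outcome recording, score OAA/S in both arms on one common timetable from the start of sedation, for example by adding the existing PCS timetable to the TCIS titration checks. Base the between-arm over-sedation comparison on those common scores only, and log episodes seen at other times separately. No clinical rule changes.

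**Cost.** Protocol and chart wording; the chart already has 5-minute OAA/S cells and vital signs are already taken every 5 minutes. If OAA/S 3 is reached at 10 min, TCIS gains about 3 to 5 scores per patient: 15, 20 and 25 min, plus 5 and 10 min where these do not coincide with titration checks. Other titration times can add a few more, because the later 20-minute scores then fall off the common clock. The protocol should state the downside: extra scoring adds stimulation in TCIS and may lead to target reductions under the existing over-sedation rule, which could slightly affect propofol use.

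**If the timetables are kept.** Report over-sedation descriptively, with each arm's schedule and whether unscheduled observations count. Limiting the comparison to after 30 min reduces the difference in detection but does not fully remove it (0.22 against 0.22–0.28 at 120 min, and TCIS titration may run past 30 min). It also gives up the early comparison.
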